#### Secondary outcome variables.

Dyspnea was assessed using the University of California, San Diego Shortness of Breath Questionnaire (UCSD SOBQ, secondary primary outcome) and the Modified Medical Research Council Dyspnea Scale (mMRC), respiratory health status by COPD Assessment Test (CAT) and clinical COPD questionnaire (CCQ). Cough and sputum symptoms were measured by the Cough and Sputum Assessment Questionnaire (CASA-Q). Functional capacity was measured by 6-minute walk distance (6MWD). Information on exacerbations was collected by monthly telephone calls. Moderate exacerbations were defined as those requiring use of systemic steroids and/or antibiotics or urgent health care visit; and severe exacerbations were those requiring emergency department (ED) visit or hospitalization. Pulmonary function was measured as FEV1 and FEV1% predicted according to ATS guidelines.

#### Clinical and Exposure Assessments.

Demographics, smoking history, comorbidities, medication use, and body mass index (BMI) were assessed. Participants kept a daily Time Activity Diary (TAD) during each week of sampling to track time spent indoors and home smoking behaviors. Indoor air quality was monitored over a one-week period, at each monitoring period, in the room the participant reported spending the most awake time. Measurements included PM2.5 and particles with diameter less than 10  $\mu\text{m}$  (PM10), nitrogen dioxide (NO2), and airborne nicotine. Residential addresses were geocoded to assess census tract poverty rate. Active smoking during study was determined by self-report number of cigarettes smoked per day and salivary cotinine. Smoking in the home was measured by air nicotine, daily report of anyone smoking in home, number of people smoking, and number of cigarettes smoked in home, averaged over the week.

**Lung Function:** Pulmonary function testing was assessed as FEV1 and FEV1% predicted, that is FEV1, adjusted for age, height, and sex. This was performed according to ATS guidelines using a KOKO® (Pulmonary Data Services, Inc., Louisville, CO) pneumotach connected to a laptop computer. Predicted values for FEV1 and FVC were calculated by formulae of Hankinson, et al. At each examination 3 sets of values will be obtained, and the highest set of FEV1 and FVC measurements were used in the analysis.

### **Outcomes for Specific Aim #2 (Markers of inflammation and oxidative stress).**

**Blood:** Blood was collected, and several systemic markers of inflammation were selected based on their relevance to long-term outcomes in COPD and air pollution. For example, serum leukocytes, CRP, TNF $\alpha$ , IL-6 and IL-8 have been found to be elevated in subjects with COPD and CRP and TNF $\alpha$  have been associated with exacerbations and disease severity; CRP, IL-6 and IL-8 have been associated with annual decline in lung function in individuals with COPD; and fibrinogen has been linked with worse COPD severity and future mortality. In addition to their relevance to COPD, these systemic markers of inflammation have been selected because of their relevance to air pollution (this will include analysis of complete blood count-CBC). Specifically, PM and poor indoor air quality have been associated with increased pro-inflammatory cytokines TNF $\alpha$  , IL-6, IL-8, IFN $\gamma$  and CRP. Serum was stored at -80°C.

**Markers of oxidative stress:** Have been associated with COPD and environmental exposures. 8-Isoprostanate will be analyzed in serum, and urine using 8-isoprostanate F2a Assay Kit.

**Urine:** Was collected for measurement of markers of inflammation, including 8-isoprostanate, as this marker has been shown to be elevated during exacerbations of COPD and has been linked with environmental exposures, including SHS and PM.

### **Additional Participant Characterization.**

A baseline survey was administered to document respiratory status and COPD severity, using survey tools described above. In addition, the baseline survey collected information on:

**Demographics:** Age, gender, race/ethnicity, socioeconomics stats (SES) including education, employment, marital status, household income, and type of health insurance; family history of lung disease, dietary patterns.

**Comorbid illnesses** associated with COPD or that can worsen was assessed by self-report in questionnaire, including gastroesophageal reflux, cardiovascular disease, osteoporosis, diabetes, depression/anxiety using the Hospital Anxiety and Depression Scale (HADS), and others.

**Home and Other Environment Characteristics:** Detailed questions about the current environment was collected with surveys developed from our previous studies. Questions determined exposure to SHS (number of cigarettes smokes in home, by whom), self-reported evidence of mold, evidence of moisture problems, exposure to pets, pests, and other key indoor environmental exposures.

**Anthropometric Measurements** including height, weight for calculation of body mass index (BMI).

**Nicotine dependence** measured using the Fagerstrom Test for Nicotine Dependence which is a standard instrument for assessing intensity of physical addiction to nicotine.

**Smoking status and quantity.** Salivary cotinine was measured to assess smoking status at each visit and to provide a quantitative assessment of exposure.

Social Cognitive measures: For each SCT construct, participants were asked to rate how much confidence, importance, and motivation they had to implement a home smoking ban or quit smoking on a 10-point scale, where 1 is “not at all sure, not at all important, don’t want to do it at all”, 10 is “completely sure, extremely important, really want to do it every day”, and 5 is “somewhere in between”. We administered our previously validated measure of SHS positive and negative expectancies and knowledge of SHSe harm, which has been shown to be associated with SHS air nicotine levels.

## Analytical approach

We used descriptive statistics to characterize the patient sample, using proportions or means with standard deviations where appropriate. Descriptive statistics of central tendency and variability were generated. The distributions of each variable were assessed for normality, and appropriate transformations were made as necessary.

Primary analysis included an Intention-to-Treat analysis including all subjects randomized and having data at baseline and 6-month. The primary outcome measured included SGRQ score, and the secondary primary outcome, dyspnea, UCSD SOBQ. These outcomes were selected based on preliminary data showing an association with pollutant exposure and because they are measured with standardized instruments, which allowed for comparability across clinical trials. Furthermore, patient-reported outcomes provide insight into the practical effects of disease on everyday life and dyspnea is the primary reason for patients seeking medical care.

Secondary outcome measures included: CAT score, FEV1 and % change in FEV1 after albuterol. In addition, we evaluated respiratory exacerbations which were defined as a worsening of respiratory symptoms requiring antibiotics or oral corticosteroid use and acute health care utilization. The primary outcome for Specific Aim #2 is serum CRP concentrations, however several inflammatory and oxidative stress markers as outlined above will be measured.

In order to compare the change over time in our outcomes between treatment groups, analyses will consist of generalized linear mixed model (GLMM) to account for within-person correlations of the outcome. For the primary outcome measure we used a linear model:

$$E[Y_{ij}] = b_0 + b_1 \text{visit}_j + b_2 \text{treat}_i + b_3 \text{treat}_i * \text{visit}_j + a' \text{visit}_j * z_i$$

where  $Y_{ij}$  is the total SGRQ score for the  $i^{\text{th}}$  individual on the visit  $j$ ,  $\text{treat}_i$  is the treatment group indicator,  $\text{visit}_j$  is a numeric visit number, and  $z_i$  is a vector of potential baseline covariates. The parameter  $b_3$  is the parameter of interest as it quantifies the effect of treatment on reducing COPD symptoms over time. For the analyses of respiratory exacerbations, we used cross-sectional logistic regression of exacerbation event (yes/no) over the course of 6-month follow-up on treatment group, adjusted by the potential baseline covariates; the parameter of interest was the odds ratio of the treatment group, as it represents the effect of treatment on the likelihood of having COPD-related exacerbations.

**Confounding:** Models above were constructed with and without adjustment for baseline covariates not adequately balanced after randomization and potential prognostic factors. Some potential covariate candidates included age, gender, race, other air pollutants (e.g., ambient pollutant concentrations), climate factors (temperature, humidity), season of recruitment, social

factors (e.g., educational attainment, household income), disease severity, medication use including inhaled corticosteroid use (participants were encouraged to bring their medications to visits), smoking pack-years, presence of HCSB, smoking status and quantity of active cigarette smoking (measured by self-report and salivary cotinine), and baseline level of the outcome.

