Cover Page

Record (NCT) Identifier Number: NCT03658538

Johns Hopkins University
Unique Protocol ID: IRB00185955

Study Title: Motivational Interviewing and Air Cleaners for Smokers With COPD (MOVE COPD)

Principal Investigator: [name]

Protocol Date: February 4, 2022

MOVE COPD Study Protocol

Objectives

Specific Aim #1: To determine whether a multi-component environmental intervention to improve home air quality (PM, SHS and NO₂ reduction) will improve respiratory morbidity (i.e., symptoms, quality of life, lung function and reduce risk of exacerbations) in smokers with COPD.

Specific Aim #2: To determine whether a multi-component environmental intervention to improve home air quality (PM, SHS and NO₂ reduction) will be associated with intermediate outcome measures known to be linked with long term outcomes in COPD, including airway (induced sputum) and systemic (serum and urine) markers of inflammation and oxidative stress, in smokers with COPD.

Study Procedures

1. Study design, including the sequence and timing of study procedures.

We will recruit current smokers (n=150) with moderate to severe COPD and those still smoking after a one-month smoking cessation run-in period will be randomized (estimated 80% of original sample, goal n=120) to receive either 1) air cleaner (with HEPA filters for reduction of PM) and MI for SHS reduction or 2) sham air cleaners. All eligible participants will be offered smoking cessation counseling throughout the study period and will have air monitoring and outcomes assessed at randomization, and 3 and 6-months post intervention. All patients enrolled in this study will continue to have their usual care for COPD as determined by their primary care provider or their usual COPD caregiver. No treatments will be discontinued.

2. Screening Assessment Visit

The initial clinic visit will take place at the Johns Hopkins Asthma and Allergy Center. During the initial clinic visit participant eligibility will be established and informed consent obtained. The screening assessment visit is expected to take approximately 2 hours.

The screening assessment visit will include the following:

- Informed consent
- Pre- and Post-BD spirometry
- Eligibility assessment questionnaires
- Clinical Examination to include anthropometry, vitals and skinfold assessment

3. Home Air Quality Screening Assessment (IF APPLICABLE)

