In addition, we will have a home air quality screening assessment visit prior to enrollment in the home of participants who have a “home smoking ban” in order to ensure that we randomize homes that have elevated PM values that are more likely to benefit from the intervention of air cleaners to improve indoor air quality. To determine further eligibility, we will place an air pollution monitor in the home (room where the participant reports spending most of his/her time) up to 7 days to measure the air quality. Only participants residing in homes with PM_{2.5} values $\geq 10 \mu\text{g}/\text{m}^3$ (National Ambient Air Quality Standards (NAAQS) set by the EPA for annual ambient PM_{2.5} and slightly above WHO standards of $10 \mu\text{g}/\text{m}^3$ for annual indoor PM_{2.5}) will be included. In the case, where we register MIE values borderlines 8-10, we will repeat the MIE assessment only if the participant agree. We will continue to not require home monitoring for homes where smoking is allowed indoors given that PM levels will likely to be elevated.

4. Run-In Period (1 month)

All enrolled will be given two Motivational Interviewing sessions for smoking cessation during the run-in period. Participants will receive 1 in-person session and 1 phone call session. Nicotine replacement therapy (NRT) will be offered during this period to all participants following approval by a study physician (a pulmonary attending or fellow). Referrals to community resources for additional support will also be provided.

Individuals who quit smoking during the 1 month run-in (self-report 7 day abstinence) will not be randomized nor included in intent-to-treat analyses to maintain adequate power to determine whether pollutant reduction in those who actively smoke provides health benefit. However, if participant would like to continue receiving smoking cessation counseling and NRT they will be referred to the community resources provided during the Motivational Interviewing session. No additional clinic and home visits will be done. An active air cleaner will be offered to ensure there is no incentive to continue smoking and to optimize continued smoking abstinence.

Individuals who continue to smoke (self-report) at the conclusion of the run-in period will be randomized.

5. Home Visits: Exposure Assessment Methods

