Time Activity Diary (TAD): Participants will be asked to keep a simple TAD during each week of sampling. TAD will collect information on participant location (indoor/outdoor/in vehicle, home/work/other), and indoor activities which are gas and particle generating such as cooking, heating, smoking, burning incense or candles. We will adapt TADs previously designed and used for our previous air pollution exposure assessments.

Indoor Air Monitoring: Will be conducted for assessing:

Airborne PM2.5 fine and PM2.5-10- coarse, conducting gravimetric analysis using time-integrated filter based sampler or using a commercially-available low cost PM sensor.

Temperature and Humidity are also monitored.

Ultrafine Particles (UFP) will be measured at high temporal resolution using a Partector (CH Technologies). This device measures lung deposited surface area, which is dominated by particles with diameter less than 100 nm.

Airborne NO₂ will be measured with passive samplers (Ogawa badges) using standard methods. Temperature and humidity will also be recorded to adjust NO₂ analytical results. All NO₂ samples will include 10% blanks and duplicates and will be blank corrected. NO₂ samples will be analyzed spectrophotometrically.

Airborne nicotine will be monitored using passive sampling badges according to standard methods. Nicotine is collected by passive diffusion onto glass fiber filter treated with 4% sodium bisulfate solution. The cassette is then sealed and transported back to the laboratory for extraction and analysis using GC-MS, Shimadzu GC-17A, QP 5000, (Shimadzu Corporation, Japan).

Outdoor Air Monitoring: Will be conducted for PM_{2.5} and NO₂ with similar methods as described above for indoor monitoring. Monitors will be placed in a convenient and secured location outside of homes to measure air quality. The monitoring machines will run day and night during each of the 3 periods of seven days of monitoring. While they run, they make no more noise than a pump in a fish tank. We will give you the results of the air quality test after the study is completed

± We will provide participants the results of the air quality test after the study is completed.

**** If the participant is unable to attend their clinic visit, questionnaires and data collection may occur at home and/or by phone with the exception of six-minute walk and albuterol administration for spirometry.*

6. Clinical Visits: Outcomes Assessment

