Smoking Cessation counseling and Nicotine Replacement Therapy (NRT): Smoking Cessation counseling will be offered to all eligible participants throughout the study. Study will offer NRT to all participants during the Run-In period. If participants would like to continue NRT after the Run-In period they will be referred to the community resources provided during the Motivational Interviewing session.

Participants in the control group will receive 4 sessions of education smoking cessation counseling as an attention control condition. Cognitive based therapy will be provided to participants and will focus on anticipating triggers for relapse and developing coping strategies to deal with withdrawal. Problem solving and skills training will be integrated to support cessation. Participants will be paid \$25 for completing all four sessions to ensure completion. These incentives are provided regardless of behavior change and are included in this efficacy study to evaluate whether a full dose of intervention results in meaningful changes in behavior.

11. Definition of treatment failure or participant removal criteria.

Participants may be removed from the study early if they are not living in their home during the study time (including admission to the hospital). In these cases, monitoring of the home environment would not reflect exposure.

12. Description of what happens to participants receiving therapy when study ends or if a participant's participation in the study ends prematurely.

At the end of the study, participants in the control group will also receive active air cleaners.

13. Inclusion/Exclusion Criteria

Inclusion Criteria:

- 1) Age \geq 40 years,
- 2) Physician diagnosis of COPD,
- 3) GOLD Stage II-IV disease with (post-bronchodilator) FEV1/FVC $<$ 70% and FEV1 (% predicted) $<$ 80%. *IF FEV1/FVC < 70% and FEV1 (% predicted) \geq 80%, additional requirement will apply/will be asked: CAT score \geq 10 OR exacerbation history during the last 12 months. Also, IF available for screening purposes: participant can provide a previous PFT report within the last 6 months.*
- 4) Tobacco exposure \geq 10 pack-years, and

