**The primary outcome was health-related QOL determined using St. George's Respiratory Questionnaire (SGRQ).**

**Quality of Life:** Health-related QOL was determined using the St. George's Respiratory Questionnaire (SGRQ). The SGRQ is a disease specific instrument that contains 50 items in three subscales (symptoms, activity, and impact). Each response has an empirically derived weight, and the total score is calculated from responses to all 50 items.

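### The primary analysis is called intention-to-treat but admits only participants with baseline and 6-month data, which makes it a completer analysis that can be biased if loss follows worsening

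*SAP*

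**What the plan says.** The primary outcome is the SGRQ (SAP, Primary outcome variable). On the analysis set, the SAP (Analytical approach) says: "Primary analysis included an Intention-to-Treat analysis including all subjects randomized and having data at baseline and 6-month". On the model, it says that "analyses will consist of generalized linear mixed model (GLMM) to account for within-person correlations of the outcome". The treatment effect is b3, the treatment-by-visit slope, where visit "is a numeric visit number".

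Four protocol statements bear on this:

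- Study design: participants "will have air monitoring and outcomes assessed at randomization, and 3 and 6-months post intervention". A 3-month SGRQ is therefore planned for everyone randomized.
- Run-In Period: those who quit smoking during the run-in "will not be randomized nor included in intent-to-treat analyses to maintain adequate power". This is the only exclusion from intention-to-treat analyses that the protocol names, and it happens before randomization.
- Participant removal criteria (section 11): participants may be "removed from the study early if they are not living in their home during the study time (including admission to the hospital".
- Note on missed clinic visits (end of section 5): "If the participant is unable to attend their clinic visit, questionnaires and data collection may occur at home and/or by phone".

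The text available for review contains no post-randomization dropout allowance, no missing-data assumption or method, and no sensitivity analysis. A small part of the SAP was not available.

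**The concern.** Membership of the primary set depends on something that happens after allocation and that treatment or disease course can influence. Randomization no longer guarantees that the compared groups are alike. The 6-month condition appears only in the SAP and has no counterpart in the protocol's own exclusion.

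The restriction also discards data that the chosen model can use. A participant with baseline and 3-month SGRQ contributes to a likelihood-based mixed model without a 6-month value, and the 3-month value carries the information about worsening that may explain the loss.

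Two things are at stake. A reader would credit the result with the protection of intention-to-treat when it lacks it. And if loss follows worsening, the estimate can be biased when treatment works or when the dependence differs by arm. The direction depends on which arm loses its worsening participants.

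**Working it through.** **1. The plan's own power figure.** From SAP, POWER: 60 per arm, difference 1.75, residual SD 6.3, correlation 0.86, two-sided 0.05.

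- SD of change = 6.3 × √(2 × (1 − 0.86)) = 3.33.
- SE = 3.33 × √(2/60) = 0.609.
- 1.75/0.609 = 2.87; less 1.96 = 0.91, so power is 0.82 (0.814 with the noncentral t). The stated 80% reproduces.

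That figure assumes all 60 per arm are analysed. On the same inputs, a completer set after assumed loss of 5%, 10% or 20% gives power 0.800, 0.779 or 0.730. (6.3 is close to 16.7 × √0.14 = 6.25, so the correlation seems to be used twice. That is a separate point, and the simulations below start from SD 16.7.)

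**2. Why completers are a selected group.** With SD σ = 16.7 and equal correlation ρ = 0.86 between visits (compound symmetry is assumed):

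- Variance of any change from baseline = 2σ²(1 − ρ), so its SD = 16.7 × √0.28 = 8.84.
- Covariance of the 3-month and 6-month changes = σ²(1 − ρ), so their correlation is 0.5.

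If loss removes people who have worsened at month 3, the mean 6-month change among those left shifts by half the shift in their mean 3-month change. The contrast is biased when that shift differs between arms.

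**3. Size.** Simulation of 1,000,000 per arm. True benefit is 4.0 at months 3 and 6 (4 is the SAP's minimal important difference), with benefit shown as positive. Loss is logistic in the standardized change from baseline. All dropout inputs are assumptions. Monte Carlo SE before loss = 8.84 × √(2/1,000,000) = 0.0125.

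| Loss pattern (assumed) | Loss per arm | Completers | All available, visit categorical |
|---|---|---|---|
| Same rule, driven by 3-month change, slopes 0.3 to 2.0 | 8–21% | 3.97 down to 3.58 | 4.00 within noise |
| Same rule, no true effect | similar | about 0 | about 0 |
| Control arm only, slopes 1.0 and 2.0 (stress case) | about 15% | 3.47 and 3.04 | 3.98–4.02 |
| Control arm only, slopes 1.0 and 2.0 (stress case) | about 30% | 2.86 and 2.27 | 3.98–4.02 |
| Active arm only, slope 2.0 (stress case) | about 30% | 5.71 | 3.99 |
| Same rule, driven by the unseen 6-month change, slopes 0.9 and 2.0 | 11–23% | 3.70–3.72 and 3.08 | 3.78–3.80 and 3.33 |

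In the one-arm rows the other arm loses the same share at random. Figures in those rows move by about 0.1 with the exact loss setting.

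At the design difference of 1.75, the same common rules give completer estimates of 1.55–1.73. A separate set of runs at 1.75 let the effect grow linearly and multiplied the odds of loss by 1.5 to 2.0 per 4-point worsening at month 3. With 20% loss in control and 10% in active, completers give 1.43 to 1.29. Reversing the rates gives 2.07 to 2.20. The all-data analysis gives about 1.75 in both.

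**4. Precision.** With no loss, SE = 8.84 × √(2/60) = 1.61. At 11–15% loss it is 1.73 for completers and 1.70 for all available data. The gain from the fix is small; its purpose is bias and labelling.

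**5. Numeric visit.** For three equally spaced visits the least-squares slope has weights −0.5, 0, +0.5, so 2 × b3 is the month-6 minus month-0 contrast for participants with all three visits. Once people with only months 0 and 3 are added, the slope extrapolates their early change to month 6. For a constant true 4.0 this gives 4.07–4.20, and up to about 4.4 at 30% loss. It is 3.99–4.00 only if the effect grows linearly. Widening the population and keeping numeric visit would therefore introduce a small error of its own.

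**The case against.** - **The restriction is disclosed in the same sentence as the label.** True for a reader of the SAP. A reader of a report that carries only the label would not see it, and the label remains wrong.
- **Under a common rule the bias is small.** It is 0 to 0.4 points against an SE of about 1.7, nil under no effect, and only about 0.02–0.2 at the design difference of 1.75. This stands.
- **The large figures need one-sided dependence, and the design works against it.** Sham cleaners match the active ones in noise, airflow and appearance; both arms get four calls and the same payment; and everyone receives active cleaners at the end. No document supports 30% loss. This stands, so those rows are stress cases. Differential loss is not excluded, because only the active arm receives the home-ban counselling.
- **The removal clause is weak evidence.** Removal is optional, its stated reason is exposure measurement, and an admission may be for any cause. This stands in part: the clause makes health-related loss plausible without showing it. Home or phone collection should reduce loss, but it does not alter the analysis set.
- **Changing the model form alters the parameter that was named and powered.** That is a real cost, and much of the SAP is in the past tense, so the change may be post hoc. The central correction (population and label) does not depend on it, but item 5 of the working shows why the two belong together.

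**Conclusion.** The point holds. As written, the primary set is a completer set under an intention-to-treat label, and nothing in the available text overrides it. That part is certain and independent of any dropout assumption.

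The bias is conditional. On the SAP's SD and correlation with assumed loss, it runs from nil (no effect, common rule), through up to about 0.4 points on a true 4.0 (common rule driven by 3-month worsening), to 0.5–1.7 points in either direction if health-related loss is confined to one arm. The upper end is comparable with the SAP's 1.75-point design difference. If loss depends on the unseen 6-month value, using all available data reduces the bias but does not remove it. This should be fixed; it does not by itself invalidate the trial.

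**What to change.** 1. Define the primary population as all randomized participants, analysed as assigned, with every available SGRQ value (baseline, 3 and 6 months) in a likelihood-based mixed model.
2. Code visit as categorical, make the 6-month treatment contrast primary, and state that it replaces the numeric-visit slope b3.
3. State the missing-at-random assumption.
4. Keep the present set as a sensitivity analysis and call it a completer analysis.
5. Add a missing-not-at-random sensitivity analysis, for example delta-adjusted with delta allowed to differ by arm.
6. Report loss and its reasons by arm, and state whether the SGRQ was sought by phone from participants who had been removed.

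The cost is SAP rewording, a changed primary model form and one added sensitivity analysis. No new data are needed. If results already exist, the analysis must be rerun and the change disclosed, with the b3 result shown alongside. If the change of model form is judged too late, items 1 and 3–6 still correct the main defect, with the 6-month contrast reported as supportive.

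### The printed mixed model adjusts for the baseline outcome only through a visit-by-baseline term, which gains nothing or loses precision depending on visit numbering; the scale of b3 also depends on a coding the SAP does not state

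*SAP*

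**What the plan says.** The SAP (Analytical approach) models SGRQ on visit, treatment, their product, and a covariate vector multiplied by visit. Of b3 it says that it "is the parameter of interest as it quantifies the effect of treatment on reducing COPD symptoms over time". Visit "is a numeric visit number", and z "is a vector of potential baseline covariates". The equation has no main effect for z. The Confounding paragraph ends its list of candidate covariates with "and baseline level of the outcome". Models are fitted with and without adjustment, and neither is named as primary. The SAP specifies a mixed model but gives no covariance structure, no starting number for visit and no list of the visits entered.

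On timing, the Protocol (Study Procedures, item 1) has "air monitoring and outcomes assessed at randomization, and 3 and 6-months post intervention", so there are three assessments. The SAP's primary analysis takes "all subjects randomized and having data at baseline and 6-month" and does not say whether month 3 enters the model.

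The POWER section says that Table 1 gives power for b3. It describes the SGRQ figure of 1.75 as an arm difference in change, and sets the detectable differences beside MCIDs of 4 (SGRQ) and 2 (CAT). For the second aim: "The primary outcome for Specific Aim #2 is serum CRP concentrations".

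**The concern.** There are two linked issues.

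**Baseline adjustment.** The outcome at randomisation is already collected, and adjusting for it is the cheapest precision available. With b2 free and no covariates, the test of b3 has change-score precision. A visit-by-baseline term without a main effect cannot be relied on to improve that, and its behaviour depends on whether the first visit is called 0 or 1. An analysis should not depend on that choice.

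**Scale.** A coefficient on a numeric visit is a change per visit. The POWER section treats it as the whole change and compares it with the MCID. If three consecutive visit numbers are entered, a reported b3 of -2 is a 4-point benefit at 6 months, and reading it directly against the MCID understates it by half.

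**Working it through.** **Inputs.** SAP POWER and Table 1: 60 per arm, two-sided alpha 0.05; residual SD and within-person correlation (rho) for each outcome; SGRQ SD 16.7, rho 0.86.

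**1. Which scale Table 1 uses.** Detectable difference at 80% power for a two-point change, taking the printed residual SD as given:

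(1.960 + 0.842) x residual SD x sqrt(2(1 - rho)) x sqrt(2/60)

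| Outcome | Residual SD, rho | Computed | Printed |
|---|---|---|---|
| SGRQ | 6.3, 0.86 | 1.71 | 1.75 |
| CAT | 3.7, 0.77 | 1.28 | 1.30 |
| FEV1 | 0.13, 0.94 | 0.023 | 0.024 |
| IL-8 | 1.47, 0.55 | 0.71 | 0.72 |
| CRP | 1.92, 0.32 | 1.15 | 1.15 |

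All five rows fit within rounding of the printed inputs. Table 1 is therefore on the full-change scale; read as per-visit slopes, the printed values would be about twice too large. This identifies the scale and does not validate the values. Since 16.7 x sqrt(1 - 0.86) = 6.25, the residual SD already contains rho, and the formula applies rho again. That is a separate problem.

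**2. What b3 is under each coding** (complete data, compound symmetry). With visits 0/1/2 or 1/2/3, the within-person slope is (month 6 - baseline)/2, so a 4-point 6-month benefit gives b3 = -2. Baseline and month 6 alone, kept as visits 1 and 3, also give -2. Coded 0/1 they give -4, and only then does b3 equal the quantity in the POWER section. The test statistic is the same in each case.

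**3. What the printed adjustment does.** Let D0 and D6 be the arm differences in mean outcome at baseline and month 6, and a the fitted coefficient on visit x baseline. With three visits and a random intercept, the 6-month effect is

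2 x b3 = D6 - c x D0, with c = 1 + 2a,

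and its variance is proportional to 1 + c² - 2 x rho x c. A change score has c = 1, giving 2(1 - rho). ANCOVA has c = rho, giving 1 - rho². The ratio of ANCOVA to change score is (1 + rho)/2: 0.93 for SGRQ, 0.885 for CAT, 0.97 for FEV1, 0.775 for IL-8 and 0.66 for untransformed CRP. To match ANCOVA for SGRQ, the printed term would need a = -(1 - 0.86)/2 = -0.07.

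- *Numbered from 0.* The term vanishes at baseline and a is estimated at about 0.002, so c is about 1. The simulated variance ratio to the unadjusted model is 1.01 to 1.03: no gain.
- *Numbered from 1.* One coefficient must represent regressions on baseline of 1, rho and rho by a, 2a and 3a. In simulation the estimated random-intercept variance for SGRQ collapses to about zero. Least squares then gives a = (1 + 5 x rho)/14.
  - SGRQ: a = 5.3/14 = 0.379 and c = 1.757; ratio = (1 + 3.087 - 3.022)/0.28 = 3.80.
  - CRP, by the same formula: a = 2.6/14 = 0.186 and c = 1.371; ratio = (1 + 1.881 - 0.878)/1.36 = 1.47.

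**4. Simulation** (60 per arm, complete data, compound symmetry, random-intercept REML, visits 1/2/3). Variance ratio about 3.5 to 3.9 for SGRQ and 1.4 to 1.5 for CRP. Type I error with model-based standard errors about 12% and 7 to 8%. For a true 4-point SGRQ effect with SD 16.7 and rho 0.86, power falls from 71% unadjusted to 41%.

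**5. Sensitivity to what the SAP leaves open.**
- Cluster-robust standard errors on the same fits: type I error near 5%, with the same loss of precision.
- Unstructured covariance, SGRQ: type I error near 5%, but the SD of the 6-month effect is about 6.3 against 1.7 unadjusted, and power for 4 points is 12%.
- Covariance known rather than estimated: variance ratio only 1.16 (SGRQ) and 1.22 (CRP).
- Two visits coded 0/1: ratio 1.02 and 1.08. Coded 1/2: 2.70 and 1.40, with type I error 10.5% and 9.3%.
- Baseline main effect added and the interaction kept: ratio 0.93 and 0.68; type I error 4.0 to 4.4% and 2.8 to 3.2%, because random-intercept standard errors are then too large.

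**The case against.** The intended scale can be inferred. The POWER section speaks of a difference in change, the primary set is defined by baseline and 6-month data, and Table 1 fits the full-change formula. With two visits coded 0/1, the model and POWER sections agree. This stands: a reader might infer that the SAP gives no way to tell which scale was meant, and the documents do not support that. What is missing is a stated coding, and nothing excludes month 3 from the model. Coding in months is not a fair reading either, because the SAP specifies a visit number. The scale point alone is a reporting clarification.

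The type I error result needs several conditions together: baseline actually placed in z, the equation taken literally, numbering from 1, a random intercept and model-based standard errors. The SAP lists baseline only as a candidate, also fits unadjusted models, and leaves covariance and standard errors open. This stands too. A reader might infer that the adjusted test fails to hold 5%; that does not follow from the SAP. What survives is that, as printed, the term gives no gain with numbering from 0 and a loss of precision with numbering from 1 under every covariance treatment tried.

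Finally, the gain from proper adjustment is small for SGRQ, the one outcome the trial was powered on, and the CRP figure uses an untransformed correlation although the SAP says "appropriate transformations were made as necessary". Both are correct. If the transformed correlation were 0.5 to 0.7 (an assumption), the CRP ratio would be 0.75 to 0.85, still a useful gain.

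**Conclusion.** The concern holds in a conditional form. Taken as printed, the visit-by-baseline adjustment either wastes a baseline value already in hand or reduces precision, depending on an unstated numbering. Proper adjustment would shorten the standard error by 3.6% for SGRQ (sqrt(0.93) = 0.964), 12.0% for IL-8 and 18.8% for untransformed CRP, relative to the change score.

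The harm rests on a literal equation, the baseline outcome in z, and numbering from 1; inflated type I error further requires model-based random-intercept standard errors. If the product term is shorthand that includes the main effect, the harm disappears. The factor of two in b3 requires three consecutive visit numbers (or two kept as 1 and 3), and it does not make the test invalid. The numerical results assume complete data and compound symmetry. The point merits a SAP revision; it does not show that the trial's conclusions would be wrong.

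**What to change.** Name the baseline-adjusted arm difference at 6 months, in outcome units, as the estimand. Estimate it by ANCOVA, with the baseline outcome as a covariate, or by a mixed model with categorical visit and a common baseline mean. In simulation both hold type I error at 5.1 to 5.4% and deliver the expected precision. Use the same model for SGRQ, CRP and the other continuous outcomes, on the transformed scale where one is used, and report the 3-month difference as secondary. State the visits entered, the covariance structure and the standard-error method. Put Table 1 and the MCID comparison on the 6-month scale.

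Adding a baseline main effect alone to the numeric-visit model is not enough: it leaves the precision unchanged (ratio 1.00).

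The cost is a SAP revision and one or two extra parameters, with no new data. The SAP is largely in the past tense. If results are already known, keep the planned test, report b3 converted to the 6-month scale with the coding stated, and label the baseline-adjusted model a sensitivity analysis. None of this repairs the double use of rho in Table 1, which needs its own correction.
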